Design and Measures: Once acceptability of VICTORI has been assessed through Aim 1 and modifications have been finalized, [name] and [name] will undergo fidelity training to ensure uniform usage of the simulation flow sheets and performance rubrics. Minimum passing score (i.e., performance on simulation that results in vaccine acceptance) will be established using the borderline group standard setting method.⁶⁹⁻⁷¹ The borderline group method is a well-established process for evaluating examinees that uses a checklist to assess proficiency when directly observing a performance test. VICTORI will be implemented using the same methods as described in Aim 1 for physicians and staff. VICTORI VR simulation implementation may take place over ZOOM based on the COVID-19 pandemic and institutional guidelines limiting in-person research visits. VICTORI VR simulation implementation sessions will be audio and video recorded. VICTORI's effect will be assessed using a repeated measures pre-post study design with follow-up period. We will collect monthly baseline data on HPV vaccine initiation and completion rates in PPCC for six months prior to implementing VICTORI. In phase I, VICTORI will be administered to resident and attending physicians. We will then collect HPV initiation and completion rates monthly during the time of intervention implementation and for the following six-months. To assess vaccination rates in clinic compared to HPV vaccination, we will also collect influenza, Tetanus, Diphtheria, and Pertussis (Tdap), and meningococcal conjugate (MCV4) vaccine for the six months prior and post VICTORI implementation in PPCC.

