
Data Analysis: Repeated measures generalized linear mixed-effects regression (GLMER) will be used to test whether vaccine initiation and completion rates of 9 to 17-year-old boys and girls increase in response to VICTORI. Models will include a logit link function to model the binary patient-level response of vaccine initiation (yes/no) and a random subject-specific intercept to account for patient encounters nested within physicians. Our primary outcome, determining the increase in the proportion of patients receiving HPV vaccination seen by resident and attending physicians in response to the intervention will be tested using the GLMER model including fixed-effect terms for study month (i.e., time) and period (pre-intervention vs. post-intervention). A likelihood ratio test (LRT) for period will provide a formal test of whether vaccine initiations increase in response to the intervention. Differences in the trajectory (i.e., change in slopes) of vaccine initiations between pre- and post-intervention periods will be tested by the inclusion of an interaction term for time and group. The inclusion of a random slope for time will be determined based on assessment of model fit. Polynomial terms or restricted cubic splines will be considered to model non-linear associations in vaccine initiation (i.e., capture the possible early intervention effect and subsequent decline). Additional terms as described for resident and attending physicians in phase I will be added to capture changes in the level and slope of vaccine initiation in response to training staff in phase II. Primary analyses will be conducted for

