determining whether VICTORI increases vaccine initiation. The PPCC is staffed by 80 residents and 20 attending physicians and reflects the maximum sample size for the intervention. To inform our power calculations for this proposal, we reviewed all PPCC patient visits for 11 to 17-year-old boys and girls from July 1, 2016 to June 30, 2017. HPV vaccination was initiated in 53% of visits for residents and 34% for attending physicians with greater between provider variation for residents. In addition, attending physicians saw more patients (n=9) in this age range on average per month than residents (n=2), and graphical analyses and formal regression modeling did not support material seasonal variation in initiation rates. Simulated outcomes based on these data were used to determine the minimum detectable odds ratio (OR) for vaccine initiation according to study period (i.e. pre- vs. post-intervention) as estimated from the proposed GLMER model. For resident and attending physicians combined, we assumed a total of 70 physicians having on average four patient encounters per month, a baseline probability of vaccine initiation of 43%, and a standard deviation for the subject-specific intercept of 0.55. Study power was determined to be 80% to detect an OR=1.5 based on 10k simulations. *This corresponds to a post-intervention vaccine initiation probability of 53%; or a 10% pre- to post-intervention difference.* Thus, conducting this intervention at CCHMC is expected to provide sufficient power to detect a clinically meaningful effect size for the response.

Potential Problems and Alternative Strategies: Insufficient recruitment may occur, but we do not anticipate this to be an issue as we have successfully conducted a VR intervention focused on flu vaccination with this population.²⁶ In addition, our team and expert consultants have provided extensive recommendations to recruit providers. There is the possibility of incomplete surveys; scale items with <25% missing data will be included in the analysis.⁷⁸ Multiple imputation and/or maximum likelihood estimation will be implemented should material missing values be realized for the survey responses and we will conduct a sensitivity analyses to determine the robustness of study findings to the assumptions of the imputation model.

Aim 3: Determine modifiable barriers related to HPV vaccine non-completion for future enhancement of VICTORI accordingly

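### The primary test for period has no term for clinic-wide monthly variation, so its type I error exceeds the nominal level whenever such variation exists

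*Combined protocol and SAP*

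**What the plan says.** Under Aim 2, Data Analysis, the primary model has a logit link, "fixed-effect terms for study month (i.e., time) and period (pre-intervention vs. post-intervention"), and "a random subject-specific intercept to account for patient encounters nested within physicians". The primary test follows: "A likelihood ratio test (LRT) for period will provide a formal test of whether vaccine initiations increase in response to the intervention". Two further terms are conditional: "The inclusion of a random slope for time will be determined based on assessment of model fit", and "Polynomial terms or restricted cubic splines will be considered to model non-linear associations in vaccine initiation". The section names no month-level random effect, autocorrelation term or month-robust variance. The control site (HSNHC) is modelled separately, among the secondary analyses.

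On the data, Design and Measures states "We will collect monthly baseline data on HPV vaccine initiation and completion rates in PPCC for six months prior to implementing VICTORI"; rates are then collected "monthly during the time of intervention implementation and for the following six-months". Influenza, Tdap and MCV4 rates are also collected but do not enter the test for period.

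On variation over time, Power considerations reports that in FY17 "graphical analyses and formal regression modeling did not support material seasonal variation in initiation rates". Its simulation inputs include an SD between physicians but none between months.

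**The concern.** If period changes for the whole clinic on one date, the contrast rests on a limited number of monthly clinic values, however many encounters lie behind each. Staffing, vaccine supply, visit mix or pandemic restrictions can move every physician's rate in the same month. Given month trend, period and physician, the model takes all encounters in that month as independent, so it averages such a shock away over hundreds of encounters when it does not average out at all.

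The other terms do not remove this. A linear month term absorbs a trend, not month-specific departures. Smooth splines do not follow single-month shocks. A random slope for time (presumably by physician) does not represent a shared shock. Entering month as dummies is not a way out, because a clinic-wide period would then be aliased with them.

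At stake are the standard error, confidence interval and p-value of the primary odds ratio, and the 80% power. The protocol intends these data as the foundation for an application for a multisite trial.

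**Working it through.** **Inputs from the documents.** 70 physicians, 4 encounters each a month (70 × 4 = 280), baseline 43%, physician-intercept SD 0.55, OR 1.5, stated power 80% (Power considerations); 6 months before and 6 after (Design and Measures); 1,450 FY17 visits at ages 11–17, or 1,450/12 = 121 a month (Setting and Population).

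**Assumptions.** Two-sided 5% (no alpha or sidedness is stated); one clinic-wide start; independent month effects with SD tau on the logit scale. Around 43%, tau 0.10 is 0.10 × 0.43 × 0.57 = 2.5 percentage points, and 0.20 is 4.9 points.

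**Step 1: reproduce the stated power.** Averaging p(1−p) over the physician intercepts gives about 0.230 per encounter, so one month's logit has variance v = 1/(280 × 0.230) = 0.0155. Over 12 months, period and linear month have r² = 1.5²/(11.92 × 0.25) = 0.755. The information on period is 12 × 0.25 × (1 − 0.755) = 0.734 month-units, a variance inflation of 1/(1 − 0.755) = 4.09. Then SE = √(0.0155/0.734) = 0.145, and power = Φ(0.405/0.145 − 1.96) = 80%. Simulating the planned model gave 79.0% (2,000 trials). A one-sided test gives 87% and dropping the month term gives 100%, so a two-sided 5% test with linear month is the reading that matches the plan.

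**Step 2: add clinic-wide month effects, no VICTORI effect.** The true variance of the period estimate becomes (v + tau²)/0.734 while the model reports v/0.734. The inflation factor is 1 + tau²/v, and type I error is 2Φ(−1.96/√factor).

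- 280 a month, tau 0.10: factor 1 + 0.0100/0.0155 = 1.64; type I error 12.6%.
- 280 a month, tau 0.20: factor 1 + 0.0400/0.0155 ≈ 3.57; 30.0%.
- 121 a month (v = 0.0360), tau 0.10: factor 1.28; 8.3%.
- 121 a month, tau 0.20: factor 2.11; 17.7%.

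Fitting the planned model to simulated trials agrees:

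| tau | Points | Formula, 280/month | 2,000 trials, 280/month | 500 trials, 280/month | Formula, 121/month | 2,000 trials, 121/month |
|---|---|---|---|---|---|---|
| 0 | 0 | 5.0% | 5.2% | 5.2% | 5.0% | – |
| 0.05 | 1.2 | 6.9% | 7.6% | 7.4% | 5.8% | – |
| 0.10 | 2.5 | 12.6% | 13.9% | 15.2% | 8.3% | 8.6% |
| 0.15 | 3.7 | 21.0% | 22.2% | 20.8% | 12.4% | – |
| 0.20 | 4.9 | 30.0% | 30.5% | 33.2% | 17.7% | 17.2% |

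A separate month-level check at 280 a month gave 13% at tau 0.10 and 29% at 0.20. A 3-month gap between periods changes little (13.5% at 0.10).

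**Step 3: direction.** At 280 a month and tau 0.10, 6.4% of all trials wrongly favour VICTORI, against a nominal 2.5%; the rest of the 13.9% go the other way. At tau 0.20 the figure is 14.7%.

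**Step 4: what FY17 can exclude.** One month's rate has a sampling SE of √(0.427 × 0.573/121) = 4.5 points. An 11-df test of heterogeneity between months would have about 17% power at tau 0.10 and 62% at 0.20.

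**Step 5: period by physician.** If each physician's period starts at his or her own training, some contrast arises within months. In approximate mixed-model calculations at 280 a month, type I error at tau 0.10 is 9.7% with training spread over 3 months, 8.6% over 4 and about 7.5% over 6. At 121 a month it is 6.5% over 4 months and 6.0% over 6. The spread is an assumption.

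**The case against.** The strongest reply is that the size of the problem depends on a quantity the documents never give. At tau 0 the planned test holds its level, and the only evidence on variation over time, the FY17 review, found no material seasonal pattern. Low power to see monthly variation is not evidence that it exists. This stands as a limit on the claim, but it does not clear the test: the review addressed seasonality in one year, could not exclude a tau of 0.10 to 0.20, and cannot speak for a study period in which the protocol itself plans around COVID-19 restrictions.

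The second reply is that a single start date is not established. Physicians do the simulations individually at convenient times, and the outcome concerns patients seen after participation. The control-site data run to 22 months; less 6 baseline, 6 after physicians and 6 after staff, about 4 months remain for implementation. Period may therefore be physician-specific, and months beyond the 12 modelled here are also collected. This lowers the inflation (step 5) without removing it.

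A reader might go further and infer that the plan ignores time, that its error rate certainly fails, or that the error flatters VICTORI. The documents support none of these: a linear month trend is fitted, tau is unknown, no alpha is stated, and false rejections fall about equally on both sides.

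**Conclusion.** The concern holds in conditional form. The committed model treats clinic-wide monthly shocks as independent across encounters, and nothing else in the primary analysis corrects the test for period. With one clinic-wide start, type I error at tau 0.10 is roughly 13–15% at the planned volume and 8% at the FY17 volume. It is about 7.5–10% at the planned volume if training is staggered by physician over 3 to 6 months. These figures rest on an assumed tau, a two-sided 5% level inferred from the power figure, and 6+6 months. The stated 80% is correct arithmetic, but only for tau equal to zero, which the plan does not state as an assumption. This should be fixed before analysis; given the unknown tau and the unsettled definition of period, it does not by itself invalidate the design.

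**What to change.** - Add a random intercept for calendar month, crossed with physician, to the primary GLMER. If the estimated month variance is zero, the fitted model is the present one.
- Test period by likelihood ratio against a parametric bootstrap reference. In a month-level approximation at 280 a month, the month intercept with the ordinary likelihood ratio reference brings type I error at tau 0.10 from 13% to 7%; the bootstrap is there to deal with the remainder.
- State whether period is clinic-wide or starts at each physician's training, and state the alpha and sidedness.
- Re-run the power simulation with the month term over a stated range of tau, and restate the 80%.

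The cost is one model term, a bootstrap and a re-run simulation, plus a less favourable power figure. In the same approximation, power for OR 1.5 with the month term and likelihood ratio test is about 78% at tau 0 (81% without the term) and 62% at tau 0.10, and somewhat less with the bootstrap reference.

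A t reference with months minus 3 degrees of freedom is at most a sensitivity analysis. Applied to the month-intercept model it is over-conservative when tau is 0 (1.6% type I error, 65% power), and it would be too severe if period is physician-specific. The month intercept assumes independent months. Autocorrelation would leave some inflation: a month-level t test, which holds about 5% for independent months, reaches 7.4–8.8% at an autocorrelation of 0.5.

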physicians (resident and attending combined) enrolled in both the pre- and post-intervention periods. *Secondary analyses* will examine the intervention effect on completion rates, for resident and attending physicians separately, and for all physicians and staff combined. GLMER models as described above will also be used to assess whether background rates of vaccine initiation and completion change over the study period in the absence of the intervention at the control site (HSNHC). Additional secondary analyses will focus on identifying potential mediators of the intervention effect on PPCC providers; whether the effect of the intervention is mediated by changes in the strength of vaccine recommendations and relevant theory-based constructs. Stratified analyses and formal testing of interactions will also be used to assess whether the effect of the intervention differs (i.e. effect modification) according to baseline provider characteristics such as age, sex, and attending vs. resident status, as well as patient characteristics (female vs. male patient, age of patient). As discussed, providers at HSNHC will be receiving the self-directed app-based curriculum component of VICTORI though will not participate in VR simulations and thus will not engage in deliberate practice of curricular skills. HSNHC providers survey responses will be compared to PPCC providers to assess for relevant changes in theory-based constructs including physicians' behavioral capability, self-efficacy, perceived benefits, barriers, and risk, as well as attitudes, subjective norms, and strength of recommendations that might occur following participation in the app-based curriculum only. Survey data will be collected before the app-based curriculum, immediately post-curriculum, and three months after the curriculum. This comparison will be conducted using a two-independent sample t-test.

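### The primary model has no term for physicians differing in their pre/post change, so the period test is modestly anti-conservative if response to training varies between physicians

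*Combined protocol and SAP*

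**What the plan says.** Combined protocol and SAP, Aim 2, Data Analysis. Patient-level initiation is modelled with a logit link and "a random subject-specific intercept to account for patient encounters nested within physicians". The primary model has "fixed-effect terms for study month (i.e., time) and period (pre-intervention vs. post-intervention"), and "A likelihood ratio test (LRT) for period will provide a formal test of whether vaccine initiations increase in response to the intervention". One further random effect is foreseen: "The inclusion of a random slope for time will be determined based on assessment of model fit". The primary analysis set is physicians enrolled in both periods, so each contributes a before and an after.

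No random effect for period, robust variance or cluster bootstrap is specified. Differences in response appear only among the secondary analyses, where strata and interactions are used "to assess whether the effect of the intervention differs (i.e. effect modification) according to baseline provider characteristics" and patient characteristics.

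Under Power considerations, the only between-physician variation given is "a standard deviation for the subject-specific intercept of 0.55". The result is stated as: "Study power was determined to be 80% to detect an OR=1.5 based on 10k simulations".

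**The concern.** The random intercept allows for physicians who start at different levels. It does not allow for physicians who move by different amounts. When the same physicians are compared before and after, uncertainty about the average change has two sources: encounter-level noise, and variation between physicians in the change itself. The planned model counts only the first.

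The optional slope for time does not supply the second. With balanced months, the period effect is estimated from the part of the pre/post contrast that is uncorrelated with month. A physician-specific linear trend adds nothing to the variance of that part, whereas a physician-specific step does.

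At stake is the primary odds ratio (OR): its interval would be too short and its p-value too small. The size of the problem grows with encounters per physician, so the attending-only analysis is more exposed than the resident-only one.

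**Working it through.** **Inputs from the documents.** 70 physicians, four encounters a month on average, 43% baseline, intercept SD 0.55, OR 1.5, 80% power, and workloads of 9 (attendings) and 2 (residents) a month (Power considerations). Six months before and six after (Design and Measures).

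**Assumptions.** Two-sided alpha of 0.05. A split of 20 attendings and 50 residents, which gives the stated mean: (20×9 + 50×2)/70 = 4.0. A response SD, written τ, of 0.2 to 0.5 on the logit scale; the upper end is close to the stated intercept SD.

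**Step 1: reproduce the stated power.**
- Over 12 contiguous months the centred sum of squares is 3 for period and 143 for month, with cross-product 18. Period adjusted for month keeps 3 − 18²/143 = 0.734.
- The mean of p(1−p) over the physician intercepts is about 0.231, and there are 280 encounters a month. Variance V = 1/(280 × 0.734 × 0.231) = 0.0211, so SE = 0.145.
- Power = Φ(ln 1.5/0.145 − 1.96) = 79.8%. Simulating the random-intercept model with the likelihood ratio test gives 80.1% (3,000 replicates). The plan's 80% is reproduced.
- With no variation in response, simulated type I error is 4.95% (4,000 replicates).

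**Step 2: effective number of physicians.** Over six months an attending contributes 54 encounters and a resident 12.
- n_eff = (20×54 + 50×12)² / (20×54² + 50×12²) = 1680²/65,520 = 43.
- Attendings supply 1080/1680 = 64% of encounters.
- With equal workloads n_eff = 70.

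**Step 3: add variation in response.** True variance = V + τ²/n_eff. With R = true SE/model SE, type I error = 2[1 − Φ(1.96/R)].

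| τ | τ²/43 | True SE (9/2) | R (9/2) | Type I, 9/2 | Type I, equal workloads | Type I, 9/2, 3-month gap | Honest power at OR 1.5 (9/2) |
|---|---|---|---|---|---|---|---|
| 0.2 | 0.0009 | 0.148 | 1.02 | 5.5% | 5.3% | 5.3% | 78% |
| 0.3 | 0.0021 | 0.152 | 1.05 | 6.2% | 5.7% | 5.6% | 76% |
| 0.4 | 0.0037 | 0.157 | 1.08 | 7.1% | 6.3% | 6.1% | 73% |
| 0.5 | 0.0058 | 0.164 | 1.13 | 8.2% | 7.0% | 6.7% | 70% |

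For the gap column, three months between the periods reduce 0.734 to 3 − 27²/278 = 0.378. The model SE rises to 0.202, so the omitted term is a smaller share of the total.

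**Step 4: check by simulation.**
- With 9/2 workloads, separate simulations gave 5.7% and 6.3% at τ = 0.3, and 8.1% and 7.5% at τ = 0.5. With equal workloads they gave 5.5% and 6.9% at those SDs.
- Adding the optional random time slope at τ = 0.5, 9/2, left type I error at 7.9% (2,500 replicates).
- Adding a random period effect in the same setting gave 5.2% (2,500 replicates). Physician-clustered standard errors gave 4.8% to 5.8%.

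**The case against.** The best counter-argument is that everything turns on an input the documents do not contain. No response SD is given, and at 0.2 or below the inflation is negligible. An SD of 0.5 is nearly as large as the whole baseline spread between physicians. With a zero average effect it would put 95% of physician-specific ORs between exp(−1.96×0.5) = 0.38 and exp(1.96×0.5) = 2.66, so half of the physicians would do worse after training. That is a demanding null. This stands, and it is why the size must be given as a range tied to τ. It does not remove the point, because the shortfall in the SE does not depend on the null: the interval is too short by the same factor R if training works on average. Physician-level shifts from case mix or experience would also enter the same term.

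The second argument is that 6+6 contiguous months is only the power-calculation case. Design and Measures provides for implementation months of unstated length, and these shrink the inflation if they separate the periods. This also stands, and the gap column shows it.

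Three stronger readings are tempting and are not supported:
- **That the plan expects physicians to respond differently.** Planned tests of effect modification by measured characteristics are a precaution. They do not predict residual variation.
- **That the stated 80% power is wrong.** It is reproduced under the plan's assumption of no variation in response.
- **That a random period effect should replace the random time slope.** Only adding a random period effect is supported. If physicians differ in trend rather than in step, a period term without the slope absorbs the trend and widens the interval needlessly.

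**Conclusion.** The point holds as a conditional one, and it is a cheap improvement rather than a serious flaw. The primary model omits the variance component that matters for the quantity it tests, and neither the optional time slope nor any robust variance covers it. Under two-sided 0.05, contiguous periods and the 20/50 split, type I error for a zero average effect is about 5.5% at a response SD of 0.2, rising to about 8% at 0.5. The range is about 5.3% to 7.0% with equal workloads, and about 5.3% to 6.7% with 9/2 workloads and a three-month gap. If physicians do not differ in their change, the planned test holds its 5%. A reader might infer that the trial's error rate is 6% to 8% outright; the documents do not support that, because the response SD, the alpha and the attending/resident split are all assumptions.

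**What to change.** In Aim 2, Data Analysis, prespecify a physician-level random effect for period in addition to the random intercept. Keep the optional random slope for time, and keep the random period effect in both models compared by the likelihood ratio test. Alternatively, report the period effect with physician-clustered robust standard errors; name these also as the fallback if the model does not converge. Use the same structure in the attending-only and resident-only analyses. State the alpha and sidedness in the same place.

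The cost is a few lines of text and added variance parameters. With 9/2 workloads the interval widens by about 5%, 8% and 13% at response SD 0.3, 0.4 and 0.5, and power at OR 1.5 falls from 80% to about 76%, 73% and 69–70%. There is a small convergence risk, which the fallback covers. If response does not vary, the added variance should be estimated near zero and little is lost.

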anticipate the findings to be generalizable to other urban primary care clinics that serve predominantly minority populations. The PPCC is staffed by approximately 20 attending physicians (total: 8.0 Full-time equivalent), 80 pediatric residents, 25 nurses, 21 medical assistants, 5 nurse care managers, 3 social work care managers, 3 social workers, 1 community engagement specialist, 14 community health workers, 2 customer service representatives, and 6 psychologists. Additionally, we will recruit resident and attending physicians from the HSNHC who will not receive the VR intervention but will serve as controls, only receiving the self-directed app-based curriculum. HSNHC serves a predominantly underserved population as well with 90% publicly insured. Seventy-three percent of the patient population is African American, and 5% is Latino. HSNHC is staffed by approximately 7 attending physicians (total: 2.5 Full-time equivalent) and 28 pediatric residents. HPV initiation rates in Ohio are 57% for girls and 55% for boys; completion rates are 42% for girls and 41% for boys.¹ The completion rate in Hamilton County is 16% for boys and girls combined.⁶⁸ The vaccination initiation rates in the PPCC (FY17) for 11 to 12-year-old girls was 48% (257 vaccinations initiated out of 537 visits) and for 11 to 12-year-old boys was 52% (289 vaccinations initiated out of 557 visits). The HPV vaccination initiation rate in the PPCC (FY17) for 11 to 17-year-old boys and girls was 43% (619 vaccinations initiated out of 1450 visits). The rationale for including adolescents 9 to 17 years old is this will allow us to perform a stratified analysis to determine if the intervention is more effective during the target range (11-12 years), the catch-up range (13-17 years), or early vaccination range (9-10 years). In addition, the National Immunization Survey (NIS) for Teens assesses vaccination rates in children age 13-17 years. By including all children age 9-17 years within our study population, it will allow comparison with the NIS-Teen outcome measures. The PPCC cares for very few patients 18 years and older, and we therefore did not extend our population beyond 17 years. HSNHC, environmental control, had a 51% HPV initiation rate (FY17) for 11 to 17-year-old boys and girls (183 vaccinations out of 357 visits). The HSNHC serves a comparable site to the PPCC and is similarly staffed by physicians from CCHMC though distinct from those physicians practicing at PPCC.

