Next, we will implement VICTORI with staff including nurses and medical assistants in groups of up to 15-20 participants (phase II; secondary outcome). These sessions may take place through a technology-based platform to allow for social distancing dependent on the COVID-19 pandemic and institutional guidelines limiting group meetings and in-person research visits. Staff will watch a 5-minute video on evidence-based practices in recommending the HPV vaccine and observe a facilitator and clinician participating in the VICTORI VR simulations, and then engage in a 5-minute debriefing. Staff will complete a brief pre and immediate post survey assessing their perceived benefits and barriers, subjective norms, and positive messaging about the HPV vaccine on paper or via REDCap. We will collect an additional six months of monthly HPV vaccination initiation and completion data, along with influenza, Tdap, and MCV4. We will collect the same vaccination data from the HSNHC over the same study period to serve as a control. The primary outcome will be the increase in the proportion of patients receiving HPV vaccination seen by resident and attending physicians following participation in VICTORI. Additional secondary outcomes, including physicians' behavioral capability, self-efficacy, perceived benefits, perceived barriers, perceived risk, attitudes, subjective norms, and strength of recommendations, as well as staffs' perceived benefits and barriers, subjective norms, and positive messaging will be assessed via validated survey instruments created by [name] and colleagues (see Appendix B and C).^{41,49,72-76} Physicians' strength of recommendation will be self-reported, which is a common method of measuring this construct.³⁰ In addition, this method (self-reported strength of recommendation) is supported as it is positively associated with vaccination rates documented through medical records.⁷⁷ Physician and staff demographics will also be collected to assess for moderation or confounding. Confidentiality of the results will be maintained. All surveys will have unique IDs with one REDCap form, separate from the surveys including their email and ID. Surveys will also be administered through the REDCap Database. Participants will receive a total of 3 emails encouraging survey completion prior to and following completion of VICTORI. Participants will receive a newsletter periodically via email to enhance retention and provide study updates (appendix). Powerpoint slides will be presented in clinic to as a retention tool as well (appendix).

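### Prespecify patient age band in the primary vaccination model: the protocol's own FY17 counts imply 50% initiation at 11-12 years and 21% at 13-17, and the term costs no power when the age mix is stable

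*Combined protocol and SAP*

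**What the plan says.** Aim 2, Data Analysis, describes a logistic mixed model for initiation at the patient encounter, with encounters nested in physicians. The primary test is a likelihood ratio test for period in a "GLMER model including fixed-effect terms for study month (i.e., time) and period". For non-linear time, "Polynomial terms or restricted cubic splines will be considered to model non-linear associations in vaccine initiation".

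Patient age has two other roles. Setting and Population gives the reason for enrolling ages 9 to 17 as the ability to "perform a stratified analysis to determine if the intervention is more effective during the target range (11-12 years"), the catch-up range or the early range. Data Analysis lists patient age among possible effect modifiers, in secondary analyses. Where Design and Measures speaks of confounding, it names physician and staff demographics only.

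Setting and Population gives FY17 initiation at the intervention clinic in three parts:
- "for 11 to 12-year-old girls was 48% (257 vaccinations initiated out of 537 visits")
- "for 11 to 12-year-old boys was 52% (289 vaccinations initiated out of 557 visits")
- "for 11 to 17-year-old boys and girls was 43% (619 vaccinations initiated out of 1450 visits")

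It gives no rate for 13-17 as such, and none for 9-10.

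**The concern.** The pre and post periods contain different visits, and the comparison is not randomised. The primary inference rests on the period coefficient. If initiation depends strongly on age and the share of 11-12-year-olds changes abruptly near the boundary, the period coefficient picks up part of that change. A rise in the 11-12 share would look like an effect of VICTORI, and a fall would hide one. The physician intercept does not remove this, because the mix can change within a physician's own visits.

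**Working it through.** **1. The plan's power figure.** Inputs from Power considerations: 70 physicians, four encounters a month, baseline 43%, intercept SD 0.55, OR 1.5. Six months before and six after come from Design and Measures, giving 70 × 4 × 12 = 3,360 visits. The plan does not state alpha, so two-sided 0.05 is assumed. Simulating the month-plus-period model with no gap between periods gives 79.2% power (8,000 runs) against the stated 80%. The figure reproduces, and the SD of the estimated log OR is 0.147.

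**2. Initiation by age.** This assumes that the 11-12 counts are nested in the 11-17 counts.
- 11-12 years: (257 + 289)/(537 + 557) = 546/1094 = 49.9%
- 13-17 years: (619 − 546)/(1450 − 1094) = 73/356 = 20.5%
- Odds ratio between bands: 3.86
- Share of visits at 11-12: 1094/1450 = 75.4%

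The age effect within a physician is not given and may be smaller. If the 53% (residents) and 34% (attendings) in Power considerations share a denominator with these counts, which the protocol does not confirm, a scan of every feasible split of ages between the two types gives a common within-type age OR of at least about 3.1. Sorting of ages between individual physicians could lower it further, so 2.0 is also shown.

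**3. Effect of an assumed 10-point step.** The crude rate moves by 0.10 × (0.499 − 0.205) = 2.9 points, from 42.7% to 45.6% (crude OR 1.13) or to 39.7% (crude OR 0.89). On the physician-conditional scale of the model, simulation gives 1.135 and 0.879.

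**4. False rejection with no true effect, 10-point rise** (5,000 runs per case):

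| Age OR | Setting | Without age | With age |
|---|---|---|---|
| 3.86 | Adjacent periods, 3,360 visits | 13.8% | 4.8% |
| 3.86 | 3-month gap, 3,360 visits | 9.2% | 4.9% |
| 3.86 | 3-month gap, 1,450 visits | 7.2% | 5.5% |
| 2.0 | Adjacent periods, 3,360 visits | 7.3% | 4.7% |
| 2.0 | 3-month gap, 1,450 visits | 5.3% | 5.2% |

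Monte Carlo error is at most about 1.4 points. The 3-month gap is an assumption. Design and Measures has data collected "monthly during the time of intervention implementation and for the following six-months", so implementation months lie between the periods, but no number is given. The 1,450 visits are the FY17 annual count.

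**5. Power, 10-point fall.** An age-marginal OR of 1.5 corresponds to an age-conditional OR of about 1.54. With adjacent periods and 3,360 visits:
- Stable mix: 79.6% without age, 82.4% with age.
- 10-point fall: 45.3% without age, 81.1% with age.

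For the gap with 1,450 visits, a closed form is enough. Months 6 + 6 give a variance inflation of 4.09 for period given month; with a 3-month gap it is 7.94. The standard error becomes 0.147 × √(1680/725) × √(7.94/4.09) = 0.312.
- Stable mix: Φ(ln 1.5/0.312 − 1.96) = about 26%.
- 10-point fall: OR 1.5 × 0.879 = 1.32, and Φ(ln 1.32/0.312 − 1.96) = about 14%.

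As a check on the closed form, the same formulas give 79% and 47% for adjacent periods with 3,360 visits, and false rejection of 14% and 7% for the first and third rows of the table.

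**The case against.** The strongest reply is that nothing in the documents predicts an abrupt change in age mix. Every harm figure above rests on an assumed step at the boundary. Linear drift is absorbed by the month term. Power considerations reports that FY17 initiation rates showed no material seasonal variation, and the primary analysis is limited to physicians enrolled in both periods, which limits mix change through turnover. All of this stands. It does not exclude a step worth 2.9 points in the crude rate, and the FY17 finding covers ages 11 to 17 in an earlier year.

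The plan also has partial safeguards: age-stratified and interaction analyses, comparator vaccines, optional splines, and the control clinic ("We will collect the same vaccination data from the HSNHC over the same study period to serve as a control"). None adjusts the primary period test for age. The control clinic is modelled separately and the age analyses are secondary.

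The largest figures come from adjacent periods and 3,360 visits. With a gap and FY17 volume, the distortion is much smaller. At an age OR of 2.0 in that setting it is indistinguishable from simulation error, and the gap and volume account for most of the power shortfall. This is also correct, and both settings should be read together.

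A reader might infer that the primary result will be biased, or that age mix could manufacture the design effect. The documents support neither. Even if every 11-17 visit were at 11-12 years, the crude OR would reach only 1.34, short of 1.5. A reader might also infer that an age term would make the period OR unbiased. It would not: shifts within a band, other changes in the patients seen, and an effect that differs by age all remain.

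**Conclusion.** The primary model omits a covariate that is strongly associated with the outcome in the protocol's own data and that the planned age analyses already require. Adding it is a worthwhile, low-cost strengthening, not the correction of an error or of a demonstrated bias. With a stable mix the stated 80% is unaffected, and a two-band age term leaves power at about 82%.

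If the 11-12 share stepped by 10 points at the boundary, the unadjusted period OR under no effect would be about 1.14 or 0.88. False rejection would be about 7% to 14% depending on gap and volume, or about 5% to 7% if the within-physician age OR is only 2.0. A 10-point fall would cut power from about 80% to 45% in the most favourable setting, and from about 26% to 14% with the gap and FY17 volume.

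These results rest on nested FY17 counts, a gradient that still holds in the study years, an assumed step size and gap, and two-sided 0.05. No 9-10 rate is given, so the three-band model is not quantified.

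**What to change.** In Aim 2, Data Analysis:
- Add patient age band (9-10, 11-12, 13-17) as a prespecified fixed effect in the primary model, and take the period likelihood ratio test and OR from that model.
- State that this OR is conditional on age, and that the design OR of 1.5 in Power considerations corresponds to about 1.54 on that scale.
- Report the age mix by period and by month.
- Keep the age-stratified and interaction analyses as secondary.

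The cost is a change of wording in the analysis text, with a sentence in Power considerations on the scale of the OR. No new data are needed, because age is already required for the planned stratification. The term should be fixed before outcome data are seen; adding it after an imbalance appears would be post hoc.
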